9.2 SETTING

In this NIS, data in a total of about 4600 HF patients will be collected during routine clinical practice by private practice and clinics in 8 countries.

There will be no procedure outside routine clinical practice except for handing out the KCCQs to the enrolled patients by the study staff. The physician's decision to initiate treatment with empagliflozin or

HF drug(s) with another mechanism of action is independent of the registration of the patient in this study. Empagliflozin and all other HF drugs will be prescribed according to approval.

This study is planned to observe patients treated with empagliflozin for approximately 24 weeks, whereas data of patients without empagliflozin prescription are collected at visit 1 exclusively.

In addition to data collected by the physician, all patients should fill in the KCCQ-questionnaire at visit 1, whereas only patients receiving empagliflozin must fill in the questionnaire after approximately 24 weeks to address the change in disease specific symptoms and items regarding physical functioning and self-care during empagliflozin therapy in a real-world patient population.

Since this is a real-world study, there are no specifical eligibility criteria other than life expectancy \leq 12 months and hospitalization at visit 1; patients having been enrolled into the non-empagliflozin arm must not be enrolled into the empagliflozin-arm afterwards. The contraindications and recommendations as stated in the SmPCs of empagliflozin and the other HF drugs have to be adhered to. For ethical and / or medical reasons, pregnant or lactating women, patients not willing to consent and patients with dependency relationship to the treating physician will be excluded.

9.2.1 Study sites

It is planned to collect data of approximately 4600 patients by approximately 1000 sites in 8 countries located in central east Europe (CEE): Switzerland, Poland, Romania, Hungary, Czech Republic, Bulgaria, Slovenia and Serbia). It is strived to include a minimum of about 3300 patients starting with empagliflozin treatment.

It is expected that each participating site will enroll 5 patients to ensure country-specific representativeness of collected data, so that a minimum target number of 100 patients per country will be reached.

9.2.2 Study population

Indication

Patients to be recruited within this study must have a physician diagnosed symptomatic chronic HF for which empagliflozin is an indicated treatment. Diabetic patients as well as non-diabetic patients can be enrolled.

Patients fulfilling the following eligibility criteria will be enrolled consecutively into the empagliflozin or the non-empagliflozin arm according to the physician's choice of HF treatment.

Inclusion criteria

Patients can be included if all of the following criteria are met:

- Written informed consent prior to study participation
- Male and female patients \geq 18 years at Visit 1
- Patients must be contractually capable and mentally able to understand and follow the instructions of the study personnel
- Patients with diagnosis of chronic heart failure NYHA Class 2-4

- Treatment-naïve for SGLT2i at visit 1
- Women of childbearing potential must take appropriate precautions against getting pregnant according to approval of chosen HF drug(s)

Exclusion criteria

Patients cannot be included if any of the following criteria is met:

- Missing physician's diagnosis of chronic heart failure
- Patients hospitalized at visit 1
- Life expectancy ≤ 12 months according to physician's assessment
- Lack of informed consent
- Pregnant or lactating females
- Participation in a parallel interventional clinical trial
- Chosen treatment with another SGLT2i drug than empagliflozin
- Having been enrolled into the non-empagliflozin-arm of this non-interventional study
- Current or prior treatment with SGLT2i at visit 1
- Patients with contraindications according to current SmPC
- Patients with dependency or relationship to the treating physician

9.2.3 Study visits

[Table 1](#) presents all data collected and assessments performed at each visit.

Table 1: Planned visits and data collected

Parameter	Visit 1	Visit 2
	Day 0 = index date 1 = Day of newly prescribed HF drug	24 weeks (±2 weeks) after index date 1 = End of observation [index date 2]
	All patients	Only patients treated with empagliflozin
Informed Consent	X	
Inclusion / Exclusion Criteria	X	
Patient demographics (age, gender, height, and weight)	X	X (weight only)
Medical history	X	
Alcohol consumption / Smoking status	X	
LVEF	X	X
Current NYHA Class	X	X

Table 1: Planned visits and data collected (cont.)

Parameter	Visit 1	Visit 2
	Day 0 = index date 1 = Day of newly prescribed HF drug	24 weeks (± 2 weeks) after index date 1 = End of observation [index date 2]
	All patients	Only patients treated with empagliflozin
HF related examinations according to clinical routine*	X	X
HF related Hospitalizations in the last 6 months	X	
HF medication used in the last 6 months	X	
Current HF related or other relevant concomitant medication	X	X
Prescribed HF drug at Day 0	X	X
Patient questionnaire: 23 items-KCCQ	X	X
Safety: Adverse Drug Reactions (serious and non-serious), fatal AEs, pregnancy, HF-related hospitalizations		X
Discontinuation of treatment with empagliflozin during study treatment (yes/no)		X
Intention to continue or discontinue treatment with empagliflozin after study period (yes/no)		X
Rationale for treatment discontinuation, if applicable		X

* Last available value and date when it was collected

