- Additional arguments amongst those stated before, like alternative explanation (e.g. situations where other drugs or underlying diseases appear to provide a more likely explanation for the observed event than the drug concerned).
- Disappearance of the event even though the study drug treatment continues or remains unchanged.

Intensity of adverse event

The intensity of the AE should be judged based on the following:

Mild: Awareness of sign(s) or symptom(s) which is/are easily tolerated

Moderate: Enough discomfort to cause interference with usual activity

Severe: Incapacitating or causing inability to work or to perform usual activities

Pregnancy:

In rare cases, pregnancy might occur in a NIS. Once a patient has been enrolled in the study and has taken study medication, the investigator must report any drug exposure during pregnancy in a study participant within 7 days by means of Part A of the Pregnancy Monitoring Form to the sponsor's unique entry point.

The outcome of the pregnancy associated with the drug exposure during pregnancy must be followed up and reported to the sponsor's unique entry point on the Pregnancy Monitoring Form (Part B).

The ISF will contain the Pregnancy Monitoring Form (Part A and B). As pregnancy itself is not to be reported as an AE, in the absence of an accompanying serious ADR and/or AESI, only the Pregnancy Monitoring Form and not the NIS AE form is to be completed. If there is a serious ADR and/or AESI associated with the pregnancy a NIS AE form must be completed in addition.

The study design is of non-interventional nature and the study is conducted within the conditions of the approved marketing authorization. Sufficient data from controlled interventional trials are available to support the evidence on the safety and efficacy of the studied BI drug. For this reason the following AE collection and reporting requirements have been defined.

The following must be collected by the investigator in the (e)CRF from signing the informed consent onwards until the end of the study:

- all adverse drug reactions (ADRs) (serious and non-serious),
- all AEs with fatal outcome,
- HF-related hospitalizations.

All ADRs, including those persisting after study completion must be followed up until they are resolved, have been sufficiently characterized, or no further information can be obtained.

Expedited Reporting of AEs and Drug Exposure during Pregnancy to BI Pharmacovigilance

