The following must be reported by the investigator on the NIS AE form and/or Pregnancy Monitoring Form from signing the informed consent onwards until the end of the study and provide to BI unique entry point:

All serious ADRs associated with the studied medical product empagliflozin	Immediately within 24 hours
All AEs with fatal outcome in patients exposed to studied medical product empagliflozin	Immediately within 24 hours
All non-serious ADRs associated with the studied medical product empagliflozin	7 calendar days
Drug exposure during pregnancy	7 calendar days

The same timelines apply if follow-up information becomes available for the respective events. In specific occasions the Investigator could inform the Sponsor upfront via telephone. This does not replace the requirement to complete and fax the NIS AE form.

Information required

For each reportable adverse event, the investigator should provide the information requested on the appropriate (e)CRF page and the NIS AE form.

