The following parameters will be collected at routine **visit 2** [= index date 2: 24 weeks (± 2 weeks) after index date 1] only of registered patients treated with empagliflozin:

1. Weight, BMI (will be calculated from height and weight)
2. Clinical parameters relevant for HF performed during clinical routine (last available value and date when it was collected):
 - LVEF
 - Current NYHA Class according to treating physician
 - Electrocardiogram (ECG)
 - Heart rate
 - Blood pressure (systolic, diastolic)
 - Laboratory diagnostic according to clinical routine (last available value and date when it was collected):
 - BNP (B-type natriuretic peptide) and/or pro-BNP (N-terminal pro-B-type natriuretic peptide)
 - Lipids (cholesterol, HDL, LDL)
 - Blood urea nitrogen (BUN)
 - Serum creatinine
 - Sodium, potassium
 - Complete blood count

- 6-min-walking test according to clinical routine
- 3. Current HF related or other relevant concomitant medication
- 4. HF drug(s) prescribed at visit 2
- 5. Patient reported outcomes:
 - KCCQ (23 items) completed by patients during the visit
- 6. Safety: ADRs (serious and non-serious), fatal adverse events (AEs), pregnancies, HF related hospitalizations
- 7. Discontinuation of treatment with empagliflozin during study period (yes/no)
 - If yes: date of discontinuation, reason (if applicable)
- 8. Continuation or discontinuation of treatment with empagliflozin after study period (yes/no)
 - In case of discontinuation: date of discontinuation, reason (if applicable)

The following variables have to be calculated:

BMI: Body weight [kg] / (Height [m])²

Kansas City Cardiomyopathy Questionnaire (KCCQ-23):

The Kansas City Cardiomyopathy Questionnaire Scoring Instructions

There are 10 summary scores within the KCCQ, which are calculated as follows:

1. Physical Limitation

- Code responses to each of Questions 1a-f as follows:

Extremely limited = 1
Quite a bit limited = 2
Moderately limited = 3
Slightly limited = 4
Not at all limited = 5

Limited for other reasons or did not do = <missing value>

- If at least three of Questions 1a-f are not missing, then compute

Physical Limitation Score = $100 * [(mean\ of\ Questions\ 1a-f\ actually\ answered) - 1] / 4$
(see footnote at end of this section for explanation of meaning of "actually answered")

2. Symptom Stability

- Code the response to Question 2 as follows:

Much worse = 1
Slightly worse = 2
Not changed = 3
Slightly better = 4
Much better = 5

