10. DATA ANALYSIS

Full analysis set (FAS): All registered patients who gave informed consent.

All data captured at visit 1 will be analysed for FAS.

Primary endpoint set (PES): All patients, who received at least one dose of empagliflozin for HF and have filled in KCCQ at time points index date 1 and 24 week follow-up visit. The primary endpoint will be analysed for PES.

Safety set (SAF): All patients of FAS who received empagliflozin at least once. SAF will be used for safety and further analyses.

For continuous variables number of values, mean, standard deviation, minimum, 5th percentile, 25th percentile, median 75th percentile, 95th percentile, maximum and number of missing values will be presented. For categorical variables the number and percentage with a category for missing will be given.

Percentages will be rounded to two decimal places.

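### Safety items are scheduled at visit 2 only although section 11.2 requires collection from consent onwards, and no status check is described for empagliflozin patients without a visit 2, so safety frequencies can be biased low

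*Protocol*

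**What the plan says.** **Schedule.** Protocol 9.2.3, Table 1, has two columns: visit 1 for all patients, and visit 2 at 24 ± 2 weeks for empagliflozin patients only. The row "Safety: Adverse Drug Reactions (serious and non-serious), fatal AEs, pregnancy, HF-related hospitalizations" is marked under visit 2 only. Protocol 9.3 and SAP 7 list the same content as item 6 of the visit 2 parameters; the SAP reads "Safety: ADRs (serious and non-serious), fatal adverse events (AEs), pregnancies, HF related hospitalizations".

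**Collection rule.** Protocol 11.2 has a wider window: "The following must be collected by the investigator in the (e)CRF from signing the informed consent onwards until the end of the study". The list that follows covers all ADRs, all AEs with fatal outcome, and HF-related hospitalizations. The expedited table in the same section sets 24 hours for "All serious ADRs associated with the studied medical product empagliflozin" and for "All AEs with fatal outcome in patients exposed to studied medical product empagliflozin", and 7 calendar days for non-serious ADRs and for drug exposure during pregnancy. HF-related hospitalizations are not in that table.

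**Analysis.** The SAP 10 safety set is "All patients of FAS who received empagliflozin at least once"; Protocol 9.7 agrees in substance. Neither requires a visit 2. SAP 10.3 tabulates event frequencies by system organ class and preferred term. It plans no person-time rate and no count of patients whose status is unknown.

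**Patients who leave.** SAP 9.2 has discontinuations and their reasons documented. SAP 7 censors time to discontinuation at the date of last contact.

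**The concern.** A patient who dies before week 24 has no visit 2. A patient who stopped because of an ADR, or who was admitted elsewhere, may also be less likely to attend. Read alone, Table 1 and the variable lists therefore seek safety data at a visit that the patients of most interest may not reach, while the safety set keeps those patients in the denominator.

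Section 11.2 obliges the investigator to record events but does not say how the site is to learn of them. No contact is scheduled between the two visits, and Protocol 9.2 limits non-routine procedures to handing out the KCCQ. If an event stays unknown to the site, the patient appears in the tables exactly like a patient who was followed and had no event. The denominator is fixed and missed events only lower the numerator, so any error from this source makes the safety summary look more favourable.

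**Working it through.** **Step 1: the passages side by side.**

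| Event | Table 1, Protocol 9.3, SAP 7 | 11.2, eCRF list | 11.2, expedited table |
|---|---|---|---|
| Fatal AE | visit 2 | from consent | 24 hours |
| Serious ADR | visit 2 | from consent | 24 hours |
| Non-serious ADR | visit 2 | from consent | 7 days |
| HF-related hospitalization | visit 2 | from consent | not listed |

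The schedule and section 11.2 differ for every row. Under section 11.2, an event known to the site is recorded whether or not visit 2 takes place. HF-related hospitalizations have only the eCRF duty behind them.

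**Step 2: what would reveal an event in a patient who does not return.** The SAP 9.2 discontinuation record gives a reason, and SAP 7 gives a last-contact date. Neither is a statement of vital status, hospitalization or ADR. The missing category that SAP 10 provides for categorical variables does not help, because no yes/no safety status is listed for a patient without visit 2. Item 10 at visit 1 lists the prescription date, the medication and the reason for not prescribing empagliflozin, but no confirmed intake. Safety-set membership of a non-returner is therefore not confirmed by a listed visit 1 variable.

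**Step 3: size.** The documents state no event rate, non-return rate or capture rate, so there is no planned figure to reproduce. The only documented input is about 3300 empagliflozin patients (Protocol 9.2.1). The rest are assumptions:

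- p1 = 5%, ADR risk in returners
- p2 = 10%, ADR risk in non-returners
- d = 10%, 15% or 20% without visit 2 (330, 495 or 660 of 3300)
- c = share of non-returners' ADRs captured outside visit 2

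True frequency = (1 − d)·p1 + d·p2. Reported frequency = (1 − d)·p1 + d·c·p2. Relative shortfall = 1 − reported/true.

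For d = 10%: true = 0.90 × 5 + 0.10 × 10 = 5.5%; reported at c = 0 is 0.90 × 5 = 4.5%; shortfall = 1 − 4.5/5.5 = 18%.

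| d | True | Reported, c = 0 | c = 0.5 | c = 0.9 | c = 1 |
|---|---|---|---|---|---|
| 10% | 5.50% | 4.50% (−18%) | 5.00% (−9%) | 5.40% (−1.8%) | 5.50% (0) |
| 15% | 5.75% | 4.25% (−26%) | 5.00% (−13%) | 5.60% (−2.6%) | 5.75% (0) |
| 20% | 6.00% | 4.00% (−33%) | 5.00% (−17%) | 5.80% (−3.3%) | 6.00% (0) |

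For deaths before week 24, every case is a patient without visit 2, so the relative shortfall is simply 1 − c.

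**The case against.** The strongest reply is that collection does not depend on visit 2 at all. Section 11.2 has no attendance condition and makes reporting of deaths and ADRs mandatory within fixed times. Table 1 has only two columns, so placing safety in the second, which is also the end of observation, may be a matter of layout. All treated patients is a conventional safety set. Safety is outside the primary and secondary outcomes (Protocol 9.3.2), and its analysis is descriptive. The data management and review plan, the monitoring plan and the table shells are separate documents and may already contain a status page or an unknown-status row.

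Much of this stands. A reader might infer that applying the plan exactly yields safety frequencies that are too low, with 18% to 33% as the effect. The documents do not support that: those figures assume no capture outside visit 2, contrary to section 11.2, and full capture gives no bias. A reader might also infer that the prescription date is the only drug variable at visit 1. That is wrong, since item 10 also lists the medication; what is missing is confirmed intake.

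The reply does not supply a way for the site to learn of an event. Zero bias needs complete capture in patients who do not return, and nothing in the two documents secures it. Routine monitoring is described for the highest-enrolling site in each country, so about 8 of some 1000 sites, and eCRF edit checks cannot find an event that nobody entered. A page completed from site records will not reveal events unknown to the site either, but it will separate a patient known to be event-free from one whose status is unknown.

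**Conclusion.** The concern holds as a documentary conflict plus possible under-ascertainment, not as a demonstrated bias. Table 1, Protocol 9.3 and SAP 7 conflict with section 11.2 on when safety data are collected. Events known to the site are covered by section 11.2. Events unknown to the site in patients without visit 2 are not, and HF-related hospitalizations are the most exposed because they have no expedited route. Crude frequencies over the whole safety set then count unknown status as no event, so the error can only run low.

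Under the assumed risks and 10% to 20% non-return, the ADR shortfall runs from zero with full capture, through about 2% to 3% at 90% capture and about 9% to 17% at half capture, to 18% to 33% with none. Non-return and capture decide where in that range the study falls, and neither is documented. As safety is a descriptive, non-endpoint part of this study, the change is worth making mainly because it is cheap.

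**What to change.** 1. **Reconcile the schedule.** In Table 1, Protocol 9.3 and SAP 7, mark the safety items as collected continuously from consent, in line with section 11.2, with visit 2 as the last point of enquiry.
2. **Add one eCRF end-of-observation page** for every empagliflozin patient without a visit 2, due when the visit window closes at week 26 (24 + 2) and completed from the site's own records. Fields: vital status and date last known alive; HF hospitalization yes/no; ADR yes/no; empagliflozin ever taken yes/no; or status unknown.
3. **Extend SAP 10.3.** Show each safety frequency over the full safety set and over safety-set patients with a completed safety assessment or death, with the number of unknown status in the same table. The count matters as much as the second denominator. If nothing were learned about non-returners, the second denominator would show the returners' 5.0%, still below the true 5.5% to 6.0% in the example.

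The cost is some site time for non-returners, one eCRF page, one extra table column and a schedule correction. No extra visit or procedure is needed. If the separate data management or table documents already contain these items, a cross-reference to them would replace items 2 and 3.

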9.3 VARIABLES

The following parameters will be collected at **visit 1** (= index date 1) of all registered patients:

1. Patient demographics:
 - Year of birth
 - Gender
 - Height, weight, BMI (will be calculated from height and weight)
2. Date of first diagnosis of HF
3. Etiology of heart failure
 - Coronary artery disease
 - Hypertension
 - Valve disease
 - Cardiomyopathy
 - Congenital heart disease
 - Drug induced
 - Infective
 - Storage disorders
 - Diabetes
 - Obesity
 - Other
4. Clinical parameters relevant for HF (last available value and date when it was collected) as valid at baseline and performed during clinical routine:
 - LVEF
 - Current NYHA Class according to treating physician
 - Electrocardiogram (ECG)
 - Heart rate
 - Blood pressure (systolic, diastolic)
 - Laboratory diagnostic according to clinical routine (last available value and date when it was collected):
 - BNP (B-type natriuretic peptide) and/or pro-BNP (N-terminal pro-B-type natriuretic peptide)
 - Lipids (cholesterol, HDL, LDL)
 - Blood urea nitrogen (BUN)
 - Serum creatinine

- Sodium, potassium
- Complete blood count
- 6-min-walking test according to clinical routine

5. Alcohol consumption and smoking status (non-smoker, previous smoker, current smoker)
6. Concomitant diseases / Comorbidities
 - Disease according to ICD-10 (diabetes, hypertension, coronary artery disease, infarction, chronic kidney disease, atrial fibrillation, cancer, other)
 - Date of first diagnosis
7. Previous HF hospitalizations within the last 6 months
8. HF related medication used in the last 6 months
 - Medication
 - Indication
 - Application
 - Dose
 - Start date, end date, continuing
9. Current HF related and other relevant concomitant medication
 - Medication
 - Indication
 - Application
 - Dose
 - Start date, end date, continuing
10. Newly prescribed treatment regime:
 - Date of prescription
 - Medication (empagliflozin and / or other drug)
 - Reason, if no prescription of empagliflozin
11. Patient reported outcomes:
 - KCCQ (23 items) completed by patients during the visit

The following parameters will be collected at routine **visit 2** [= index date 2: 24 weeks (± 2 weeks) after index date 1] only of registered patients treated with empagliflozin:

1. Weight, BMI (will be calculated from height and weight)
2. Clinical parameters relevant for HF performed during clinical routine (last available value and date when it was collected):
 - LVEF
 - Current NYHA Class according to treating physician
 - Electrocardiogram (ECG)
 - Heart rate
 - Blood pressure (systolic, diastolic)
 - Laboratory diagnostic according to clinical routine (last available value and date when it was collected):
 - BNP (B-type natriuretic peptide) and/or pro-BNP (N-terminal pro-B-type natriuretic peptide)

- Lipids (cholesterol, HDL, LDL)
- Blood urea nitrogen (BUN)
- Serum creatinine
- Sodium, potassium
- Complete blood count
- 6-min-walking test according to clinical routine
- 3. Current HF related or other relevant concomitant medication
- 4. HF drug(s) prescribed at visit 2
- 5. Patient reported outcomes:
 - KCCQ (23 items) completed by patients during the visit
- 6. Safety: ADRs (serious and non-serious), fatal adverse events (AEs), pregnancies, HF related hospitalizations
- 7. Discontinuation of treatment with empagliflozin during study period (yes/no)
 - If yes: date of discontinuation, reason (if applicable)
- 8. Continuation or discontinuation of treatment with empagliflozin after study period (yes/no)
 - In case of discontinuation: date of discontinuation, reason (if applicable)

